There is no minimum number of subjects required to be enrolled at a center. For the Primary Cohort, each study center will stop enrollment after they have identified a maximum of 8 subjects for whom at least 1 aDBS mode is acceptable and who enter the aDBS Evaluation Phase (~25% of the total planned number of subjects). For the Directional Stimulation Cohort, each study center will stop enrollment after they have identified a maximum of 5 subjects for whom at least 1 aDBS mode is acceptable and who enter the aDBS Evaluation Phase. The actual number of subjects at a study center may be slightly larger due to the number of subjects that are enrolled prior to cessation of enrollment. This restriction is intended to reduce the possibility that the results from one study center will be overly influential in the overall study results.

The study consists of four phases following enrollment:

- cDBS Baseline Phase (approximately 1 month): LFP Screening, Baseline cDBS and Off stimulation Assessments
- aDBS Setup and Adjustment Phase (up to 2 months): aDBS Setup visit and additional optional visits during an aDBS Adjustment period
- aDBS Evaluation Phase (approximately 2 months): One-month treatment periods in each acceptable aDBS mode with aDBS evaluation visits at the end of each period. Randomized crossover to the two investigational treatments in subjects for whom both aDBS modes were acceptable and a single treatment period in those subjects for whom only one aDBS mode was acceptable.
- Long-Term Follow Up Phase (approximately 10 months): Four scheduled visits in the preferred aDBS mode

Subject participation in an Extended Access Phase is optional and includes additional visits in the preferred aDBS mode every 6 months through commercial approval of aDBS.

The design of the Directional Stimulation Cohort is the same as the main ADAPT-PD trial. Subjects enrolled in the Directional Stimulation Cohort will follow the same visit schedule.

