9.3. Scheduled Follow-up Visit Windows

Data analyses include follow-up visits, regardless of whether the visit occurs within the window. Therefore, a late visit is preferred over a missed visit but must be accompanied by a deviation report. Follow-up visit windows are listed in [Table 4](#). Should a subject miss a visit or the visit falls outside the pre-specified window, a study deviation must be reported and the original follow-up schedule maintained for subsequent visits.

Table 4: Visit Windows

Visit	Visit ranges
LFP Screening	1-45 days after enrollment
cDBS Baseline	30-45 days after LFP Screening
aDBS Setup	1-45 days after Baseline
aDBS Adjustment	0-60 days after aDBS setup complete
Randomization / Day 0	No greater than 60 days after aDBS setup complete
aDBS Evaluation Visit 1	30-45 days after Day 0
aDBS Evaluation Visit 2*	30-45 days after Evaluation visit 1
Visit 3	45-60 days after Evaluation Visit 2 (or Evaluation Visit 1 if the subject is only configured to one aDBS mode)
Visit 4	45-60 days after Visit 3
Visit 5	90 +/- 14 days after Visit 4
Visit 6	90 +/- 14 days after Visit 5
Extended Access Visits	Every 180 +/- 60 days beginning after Visit 6 and every 6 months thereafter following the previous extended access visit

* If two aDBS modes are set up

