9.7. Enrollment and Screening Phase

This phase begins at consent and includes an Enrollment visit and an LFP Screening visit.

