- Beck Depression Inventory II (BDI-II)
- Pregnancy test (for female subjects of child-bearing potential)
- Device identification information, including historical DBS implant information
- Programming session upload to Medtronic via CDU, with BrainSense data included in the JSON session data report
- AE and device deficiency assessment

The clinician will ensure the INS device time matches that of the clinician programmer tablet (network enabled). If the INS time does not match the network time, the INS time will be updated.

The subject will be instructed on the use of the PD Home Diary. For at least 3 consecutive days in the 14 days prior to the cDBS Baseline and aDBS Evaluation visits, the subject will record, in 30-minute intervals, whether they were Asleep, “Off,” “On” without dyskinesia, “On” with non-troublesome dyskinesia, or “On” with troublesome dyskinesia. The subject will also be instructed on the use of the PKG Watch.

The subject will leave the visit on their current cDBS settings (including BrainSense settings).

9.8. cDBS Baseline Phase

This phase begins when the enrollment visit is complete and includes an LFP screening visit, cDBS Baseline period and cDBS Baseline visit.

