7.10 Safety Evaluation

The safety assessment is to characterize:

- Stimulation-related adverse events during the aDBS evaluation and the cDBS baseline phases.
- Serious adverse events, adverse events, and device deficiencies throughout the study.

Stimulation-related adverse events will be summarized during the cDBS Baseline and aDBS Evaluation Phases for all subjects, with tabulations individualized by aDBS mode in the Primary Cohort, by target site in the Primary Cohort, by lead type in the Primary Cohort, and the Directional Stimulation Cohort (DSAT analysis set). Summarized results from the Directional Stimulation Cohort will be provided as supporting analyses to the Primary Cohort results. In the Primary Cohort, if statistical comparisons of poolability across mode, lead type, and target site are accepted, overall tabulations will be provided as appropriate. To test for a difference in safety by target site (STN/GPi) and lead type, Fisher's exact test will be computed testing for differences between target sites and between lead type in the proportion

of subjects with a stimulation-related adverse event during the aDBS Evaluation Phase using data from both periods. [REDACTED]

[REDACTED]

[REDACTED]

[REDACTED]

A repeated measures logistic regression will be used to test for a difference between aDBS modes in the proportion of subjects with stimulation-related adverse events in the randomized subjects who enter the aDBS evaluation phase in the Primary Cohort. [REDACTED]

[REDACTED]

[REDACTED]

[REDACTED]

[REDACTED]

[REDACTED]

P-values >0.1 will be deemed as supporting the assumption of no target site, lead type, or mode effect, respectively, and the data will be considered poolable across the respective variable. If the p-value approaches statistical significance (defined as ≤ 0.1),¹ safety summaries will not be provided as a combined summary for that variable.

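### The stimulation-related adverse event table leaves out the Setup/Adjustment phase, where aDBS is first used, and gives no exposure-adjusted rate

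*SAP*

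**What the plan says.** SAP 7.10 opens with "The safety assessment is to characterize" and then names two items: stimulation-related events in the two treatment phases, and all adverse events, serious events and device deficiencies across the study. For the first item, "Stimulation-related adverse events will be summarized during the cDBS Baseline and aDBS Evaluation Phases for all subjects", split by aDBS mode, target site, lead type and cohort, and shown overall where poolability is accepted. Protocol 13.6 matches.

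The metrics in SAP 7.10 are number of events, number of subjects and percentage of subjects, over subject-count denominators for each phase, period and cohort. No person-time rate is mentioned.

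Under Protocol 9.9.1 and 9.9.2, aDBS is switched on at Setup, and a subject needing further adjustment goes home on one of the modes. Table 4 in Protocol 9.3 allows the adjustment period to run "0-60 days after aDBS setup complete". Acceptability is then judged on the GIC (Protocol 9.9.3, Appendix A). A mode whose side effects significantly interfere with functioning, or outweigh its efficacy, fails and is barred from Evaluation.

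The start of the cDBS Baseline Phase is given in two ways. Protocol 9.7 describes an Enrollment and Screening Phase that "includes an Enrollment visit and an LFP Screening visit". Protocol 9.8 says of the cDBS Baseline Phase: "This phase begins when the enrollment visit is complete and includes an LFP screening visit".

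**The concern.** The trial's stated purpose is to demonstrate safety as well as effectiveness (Protocol 3.2), and the endpoint rationale (Protocol 13.4.2, SAP 7.9.1.2) speaks of safety similar to cDBS for some subjects. The stimulation-related table is where a reader will look for that.

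There are two difficulties. First, the aDBS column begins only after a filter that removes poorly tolerated modes, while the aDBS exposure before the filter is in no column. Second, a percentage of subjects grows with length of follow-up, and the columns need not cover equal lengths. The first has a likely direction; the second does not.

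**Working it through.** **The plan's own safety figure.** Protocol 13.2.4 and SAP 6 state at least 95% probability of seeing an event with a true rate of 10% at least once in 30 subjects followed for about 30 days. 1 - 0.9^30 = 0.9576, so the figure reproduces for any one event type. It shows that the plan itself thinks in terms of about 30 days on aDBS.

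**Window lengths (Protocol 9.3, Table 4).**
- cDBS Baseline, starting after the enrollment visit (Protocol 9.8): (1 to 45) + (30 to 45) = 31 to 90 days.
- cDBS Baseline, starting at LFP Screening (if Protocol 9.7 puts that visit in the preceding phase): 30 to 45 days.
- One aDBS mode: 30 to 45 days. Both modes: 60 to 90 days.
- Adjustment at home: 0 to 60 days, in no column.

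Nominally (Protocol 5) the baseline is about one month, each mode one month and Evaluation about two months: 1:1 per mode, and 2:1 with aDBS the longer when modes are combined.

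**Effect of length alone.** The documents give no stimulation-related event rate. Assumption: the same constant hazard in every phase, with p30 = 10% per 30 days (the rate used in the safety sample size), range 5% to 20%. Expected percentage of subjects with an event = 1 - (1 - p30)^(days/30). At 10%: 30 d 10.0%, 31 d 10.3%, 45 d 14.6%, 60 d 19.0%, 90 d 27.1%.

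| aDBS window vs cDBS window | aDBS minus cDBS at 10% | Range, 5% to 20% |
|---|---|---|
| One mode 30 d vs 30 d (nominal) | 0 | 0 |
| Both modes 60 d vs 30 d (nominal) | +9.0 points | +4.8 to +16.0 |
| One mode 30 d vs 90 d | -17.1 | -9.3 to -28.8 |
| One mode 45 d vs 31 d | +4.3 | +2.2 to +7.9 |
| Both modes 60 d vs 90 d | -8.1 | -4.5 to -12.8 |
| Both modes 90 d vs 30 d | +17.1 | +9.3 to +28.8 |

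There is no true difference in any row. A rate per subject-month would be equal throughout.

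**Exposure that is left out.** If the full 60 days are used, the omitted share of aDBS time before long-term follow-up is 60/(60+90) = 40% to 60/(60+60) = 50% for two-mode subjects, and 60/(60+45) = 57% to 60/(60+30) = 67% for one-mode subjects. At 10% per 30 days, 60 days gives 19.0% of subjects with an event, or 0.19 x 40 = 7.6 of the 40 planned for Evaluation. With no adjustment period the figure is near zero.

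**Subjects with aDBS exposure who never enter Evaluation.** Protocol 6.1.2 estimates 70 subjects with aDBS enabled. Planned Evaluation entrants are 40 + 9 = 49 over both cohorts, or 55 + 9 = 64 at the maximum Primary Cohort size. The difference is 70 - 49 = 21 down to 70 - 64 = 6. These are planning figures, and not all such exits would be for side effects.

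**Does the all-event summary fill the gap?** SAP 7.10 also summarizes all adverse events from enrollment to exit. It promises no stimulation-related breakdown for Setup/Adjustment. It uses the As-Treated set, whose definition (SAP 7.1.3) names the Baseline, Evaluation and Long-term Follow-up phases but not Setup/Adjustment, so the attribution of that phase's events to a treatment is not defined.

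**The case against.** The strongest reply is that nothing is being compared. The aim is to characterize, and the visible safety tests concern target site, lead type and aDBS mode. The between-mode test is in randomized subjects, with the same window for each mode. That stands: a reader might infer a biased formal safety test, and there is none.

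A reader might also infer that a longer cDBS window makes aDBS look safer. The documents do not support a fixed direction. By mode the nominal windows are equal, and with modes combined aDBS has the longer one. In addition, about half of enrolled subjects are expected to exit at LFP Screening (Synopsis, Sample Size), and the table is for all subjects. Under the 31-90 day reading, averaging the two halves gives (0.35 + 10.3)/2 = 5.3% to (14.6 + 27.1)/2 = 20.9% for cDBS, where 0.35% is one day at the same hazard. This lowers the cDBS percentage, and it is a further reason to report person-time.

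Nor does one unacceptable mode remove a subject. Under Protocol 9.9.3 that subject completes a period in the other mode; only those with neither mode acceptable exit. What disappears from the column is the failed mode's experience.

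Events in Setup/Adjustment are not lost either. They are collected from consent (Protocol 11.1), classified for relation to stimulation (11.5.1), adjudicated when related (12.2), and included in the all-event summary. What is missing is their display as stimulation-related events on aDBS.

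Finally, subjects enter as responders on stable cDBS, so the cDBS column is selected as well, and merging aDBS titration into the contrast would be uneven. That is fair, and it argues for a separate Setup/Adjustment column. Transient effects that resolve before the subject leaves a visit are not adverse events (Protocol 11.4), so such a column would not be filled with passing programming effects.

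**Conclusion.** The point holds as a reporting gap in a descriptive table. The stimulation-related summary omits the phase in which aDBS is first used, and the aDBS column is conditioned on having passed a tolerability screen, so it tends to understate aDBS events. This assumes that some of the side effects behind GIC failures are recorded as stimulation-related adverse events. The amount cannot be computed, because the documents give neither an event rate nor a GIC failure rate; the omitted exposure is up to 60 days per subject.

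Separately, unequal windows can shift the percentage by about -17 to +17 points at an assumed 10% per 30 days (about 9 points either way at 5%, about 29 at 20%). These are extremes of the allowed windows, not expected values, and the net direction is undetermined.

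**What to change.** In SAP 7.10 and Protocol 13.6:

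1. Add a stimulation-related column for Setup/Adjustment, by mode in use when the event began, with all subjects in whom aDBS was enabled as the denominator. State how the As-Treated set assigns treatment in that phase.
2. Report stimulation-related events per subject-month beside the percentages for each phase and mode.
3. Show the cDBS column a second time for the subjects who received aDBS.
4. Reconcile Protocol 9.7 with 9.8 so that the cDBS Baseline Phase has one start.

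The cost is a few extra table columns from data already collected. The aDBS safety figures may look slightly less favourable.

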Secondary Endpoint	Decreased total electrical energy delivered (TEED) during the respective aDBS Evaluation Period as compared with cDBS during the cDBS Baseline Phase.
Safety Analyses	
 Stimulation-related adverse events during the cDBS baseline and aDBS evaluation phases for all subjects, with tabulations individualized by aDBS mode and by target site and combined after statistical comparisons for poolability. Serious adverse events, adverse events and device deficiencies throughout the study for all subjects.
Study Design	
Prospective, single-blind, randomized crossover, multi-center study of aDBS in subjects with Parkinson's disease.
 
The study is expected to be conducted at approximately 12 centers located in the US, Europe and Canada. It is estimated that approximately 70-100 subjects implanted with a commercially available Medtronic DBS system with Percept PC INS will be enrolled to obtain 40 subjects for whom at least 1 aDBS mode is acceptable and who enter the aDBS evaluation phase. Accounting for a 10% dropout during the aDBS Evaluation Phase, a minimum of 36 subjects (at least 8 per brain target) will complete the aDBS Evaluation phase.
 
In addition, approximately 15 subjects implanted with a commercially available Medtronic DBS system with Percept PC INS and SenSight system will be enrolled in the Directional Stimulation Cohort to obtain 9 subjects for whom at least 1 aDBS mode is acceptable and who enter the aDBS Evaluation Phase. Accounting for dropout during the aDBS Evaluation Phase, a minimum of 8 subjects will complete the aDBS Evaluation Phase.
 
Study visits and/or phases include:
 
 Enrollment Visit: Consent, Screening cDBS Baseline Phase: Local Field Potential (LFP) Screening and Baseline cDBS visits aDBS Setup and Adjustment Phase: aDBS Setup visit and additional optional visits during an aDBS Adjustment period aDBS Evaluation Phase: One-month treatment periods in each acceptable aDBS mode with aDBS evaluation visits at the end of each period. Randomized crossover to the two investigational treatments in subjects for whom both aDBS modes were acceptable and a single treatment period in those subjects for whom only one aDBS mode was acceptable.

Medtronic Business Restricted

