Since the device implant will occur outside of the study and the study requires participants to be stable on cDBS prior to enrollment, the standard deviation of the change from cDBS to aDBS in “On” time

without troublesome dyskinesia will be used to establish a threshold for assessing the performance goal. The threshold will be set as 1 standard deviation. If the difference between aDBS and cDBS (aDBS-cDBS) for a subject is at least -1 standard deviation, the threshold will be met for the subject. Using this threshold, the proportion of subjects who exceed the threshold will be computed.

The sample size was estimated using a binomial distribution for a one-sided exact test (alpha=0.0125) for a proportion (PASS 2011 module Tests for One Proportion [Differences]) to compare to a performance goal of 50%. Assuming the alternative hypothesis of 85% of subjects exceeding the threshold, a minimum of 36 subjects achieves at least 90% power to reject a performance goal of 50%.

Simulations have shown that this sample size is sufficient to cover possible deviations from normality such as a uniform distribution. The threshold criterion will remain the same as the standard deviation is robust to moderate departures from normality.

Sample size in the Primary Cohort may be increased to a maximum of 55 subjects for whom at least 1 aDBS mode is acceptable and who enter the aDBS Evaluation Phase to obtain at least 8 subjects per aDBS mode and 8 subjects per target site (Subthalamic Nucleus [STN]/ Globus Pallidus [GPi]). Criteria for increasing sample size is described in section 7.2.1.

For the safety analyses, a minimum of 30 subjects followed for approximately 30 days with aDBS out-of-clinic in the subjects' real-world environments provides at least 95% probability that all events with a true event rate of at least 10% would be reported at least once.

It is estimated that approximately 70-100 subjects implanted with a commercially available Medtronic DBS system with Percept PC INS will be enrolled in the study to obtain 40 subjects for whom at least 1 aDBS mode is acceptable and who enter the aDBS Evaluation Phase. Accounting for a 10% dropout during the aDBS Evaluation Phase, a minimum of 36 subjects (at least 8 per brain target site (STN/GPi) and 8 per aDBS mode) will complete the aDBS Evaluation phase.

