Serious adverse events, adverse events, and device deficiencies that occur from the time of enrollment through study exit/discontinuation will be summarized for all enrolled subjects. Analyses will be conducted on the AT analysis set for subjects in the Primary Cohort and on the DSAT for subjects in the Directional Stimulation Cohort. The denominator will include the appropriate number of subjects for each respective phase, period, and cohort. Events will be summarized by number of events, number of subjects who experienced the event, and percentage of subjects who experienced the event.

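### A poolability p-value of 0.1 or lower decides whether a combined summary of stimulation-related adverse events is given, so the overall per-subject rate on aDBS may go unreported

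*SAP*

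**What the plan says.** The first safety aim is to characterise stimulation-related adverse events in the cDBS Baseline and aDBS Evaluation Phases (Protocol 4.1.3 and 13.6; SAP 4.3 and 7.10). No hypothesis is attached to it.

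SAP 7.10 plans stratified tables without any condition: "with tabulations individualized by aDBS mode in the Primary Cohort, by target site in the Primary Cohort, by lead type in the Primary Cohort". The overall tables are conditional: "if statistical comparisons of poolability across mode, lead type, and target site are accepted, overall tabulations will be provided as appropriate". Target site and lead type are compared with Fisher's exact test on the proportion of subjects with an event, using both periods. Mode is compared with a repeated measures logistic regression in randomised subjects.

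The decision rule is "P-values >0.1 will be deemed as supporting the assumption of no target site, lead type, or mode effect, respectively". At 0.1 or below, "safety summaries will not be provided as a combined summary for that variable". Protocol 13.6 carries the same rule, and the Safety Analyses row of the Protocol synopsis says the tabulations are "combined after statistical comparisons for poolability".

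Serious adverse events, all adverse events and device deficiencies are handled separately and with no poolability test. SAP 7.10 says that those "that occur from the time of enrollment through study exit/discontinuation will be summarized for all enrolled subjects", and adds: "The denominator will include the appropriate number of subjects for each respective phase, period, and cohort".

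**The concern.** A significance test is being used to decide whether a descriptive safety figure is reported. Heterogeneity between modes, targets or leads is a good reason to show the strata, and these are planned anyway. It is not a reason to leave out the total, which a reader weighing risk against benefit will want in either case.

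The consequence is sharpest for mode. Subjects for whom both modes are acceptable receive both in a crossover (Protocol 9.9.3), so the same person can be counted in the dual threshold column and in the single threshold column. Without a combined summary for mode, the number of subjects with any stimulation-related event on aDBS cannot be obtained from those two columns.

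Efficacy and safety could also be presented on different footings. The trial can succeed on the two algorithms combined (Protocol 13.1, SAP 7.2), with poolability judged on the primary outcome (SAP 7.2.1). The safety pooling decision rests on a different test. A combined efficacy result could therefore stand beside a safety report with no combined stimulation-related rate.

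**Working it through.** **Inputs from the documents.** The threshold is p <= 0.1 (SAP 7.10). The plan has 40 subjects entering the aDBS Evaluation Phase, 36 completing it, and at least 8 per target site (SAP 6). The safety sample-size statement is "a minimum of 30 subjects followed for approximately 30 days with aDBS", giving at least 95% probability that an event with a true rate of 10% is reported at least once (SAP 6).

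**Assumptions.** The documents give no expected rate of stimulation-related events, no target split beyond the minimum of 8, and no lead-type split. I took 40 subjects as 8 v 32 by target and 20 v 20 by lead, event rates of 10% to 50%, a mode test at its nominal 10%, and independence of the three tests.

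**1. The plan's own figure.** 1 - 0.9^30 = 0.958, which meets the stated 95%. The figure reproduces.

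**2. What can be recovered from the planned tables.**
- Target: both leads are in the same target (Protocol 8.3), so the STN and GPi groups are disjoint and their subject counts add to a total.
- Lead type: the legacy and SenSight groups are likewise compared as separate groups, and their counts add.
- Both sums give the aDBS total only if the printed tables span both modes. The tests use both periods; the text does not say whether the tables do.
- Mode: the columns overlap. As an illustration with assumed counts, take 36 randomised subjects with 9 affected in each mode. The number with any event lies between 9 (the same people) and 9 + 9 = 18 (different people), that is 25% to 50% of 36.

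**3. Triggers with no true difference.** Exact enumeration of Fisher's test at p <= 0.1, then P(at least one) = 1 - (1 - a)(1 - b)(0.9):

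| Event rate | a: target 8 v 32 | b: lead 20 v 20 | At least one of three |
|---|---|---|---|
| 10% | 0.048 | 0.017 | 1 - 0.952 x 0.983 x 0.9 = 0.158 |
| 20% | 0.056 | 0.045 | 1 - 0.944 x 0.955 x 0.9 = 0.189 |
| 30% | 0.063 | 0.053 | 1 - 0.937 x 0.947 x 0.9 = 0.201 |
| 50% | 0.048 | 0.043 | 1 - 0.952 x 0.957 x 0.9 = 0.180 |

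This gives about 16-20%. With the 36 completers split 8 v 28 and 18 v 18, the same formula gives 14-20%. If all three tests ran at their full nominal size, it would be 1 - 0.9^3 = 27.1%; Fisher's test is conservative, so the figure is lower.

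**4. Triggers with a true target difference** (Fisher, p <= 0.1):

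| True rates | 8 v 32 | 8 v 28 |
|---|---|---|
| 40% v 20% | 0.304 | 0.284 |
| 50% v 20% | 0.491 | 0.470 |
| 60% v 20% | 0.678 | 0.659 |

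**5. What a withheld total costs in precision.** Assumed counts of 5/8 in GPi and 7/32 in STN give Fisher p = 0.039, so the combined target summary is dropped. The pooled 12/40 = 30% (95% CI 17% to 47%) is replaced by 63% (24% to 91%) and 22% (9% to 40%).

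**The case against.** The strongest reply is that little is lost. The stratified tables are unconditional, and the target and lead strata are disjoint and can be added. The target and lead tests themselves need a per-subject count over both periods, so the overall number must exist in the analysis whatever the mode test shows. All adverse events, serious events and device deficiencies are summarised for all enrolled subjects with no such test. Protocol 12.2 adds that incidence rates follow the Clinical Events Committee's determinations. No hypothesis or alpha depends on the rule.

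Much of this stands, and it limits the point to the combined stimulation-related summary. It does not remove the point. Neither the all-event summary nor Protocol 12.2 commits to a stimulation-related total on aDBS, and a count computed for a test is not the same as a reported table.

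The scope of the rule is also unclear. The withholding sentence applies to the variable that failed. The sentence on overall tabulations can be read as requiring all three tests to pass. The 16-20% figure uses the second reading. On the first, the figures with no true difference are those of each test alone: 4.8-6.3% for target, 1.7-5.3% for lead, and a nominal 10% for mode.

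Two stronger readings are tempting, and the documents do not support them.

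- A reader might infer that the overall rate vanishes exactly when safety differs. It does not: the rule triggers in only 30% of trials at 40% v 20%, and sometimes with no difference at all.
- A reader might infer that the 30-subject statement depends on the combined table, since a stratum of 8 alone would show a 10% event with probability only 1 - 0.9^8 = 0.57. That statement concerns an event being reported at least once. An event seen in any stratum still appears in that stratum's table, so splitting hides nothing. Nor does the statement mention combining modes.

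**Conclusion.** The point holds as a reporting weakness. The plan lets a noisy p-value decide whether a combined descriptive safety summary appears. What may be lost is the pooled per-subject rate of stimulation-related events on aDBS and its precision, chiefly for mode, where the columns overlap. Detection of individual events is not affected, and neither is any inferential result.

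The size is moderate: about 16-20% of trials would have at least one trigger with no true difference, and 30% to 49% would have a target trigger at true rates of 40% or 50% v 20%. These figures rest on the assumed splits, event rates, nominal mode-test size and independence, and the 16-20% also on reading one failed test as enough. The rule itself is explicit in both documents and does not depend on those assumptions.

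**What to change.** In SAP 7.10 and Protocol 13.6, delete the sentence that withholds the combined summary. Reword the conditional sentence on overall tabulations, and the matching wording in the Protocol synopsis, so that the overall Primary Cohort table for the aDBS Evaluation Phase is always given. It should show events, subjects with at least one event, and percentage, across modes, targets and leads, beside the by-mode, by-target and by-lead tables. State that each subject counts once in the overall row, and that the target and lead tables span both modes. Keep the tests only as comment on heterogeneity.

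The cost is a few sentences of text. No new data, visits or tests are needed.
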